#### 6.2.2.9. Duration of response

Duration of Response (DR) is defined, for patients with uOR, as the time from first documentation of objective response (uCR or uPR) to the date of first documentation of PD or death due to any cause. If a patient has not had an event (PD or death), DR is censored at the date of last adequate tumor or clinical assessment. The censoring rules for DR are described in Table 20.

$$\text{DR (months)} = [\text{date of event or censoring} - \text{first date of uOR} + 1] / 30.4375$$

**Table 20. Outcome and Event Dates for DR Analyses**

Scenario	Date of event/censoring	Outcome
PD or death	Date of PD or death	Event
No PD and no death	Date of last adequate tumor assessment or clinical evaluation documenting no PD	Censored

Kaplan-Meier estimates (product-limit estimates) will be presented by treatment arm together with a summary of associated statistics including the median DR time with 2-sided 95% CIs. In particular, the DR rates at 12, 24, 36, 48 and 60 months will be estimated with corresponding 2-sided 95% CIs. The CIs for the median will be calculated according to

Brookmeyer and Crowley (1982) and the CIs for the survival function estimates at the time points defined above will be derived using the log-log transformation according to Kalbfleisch and Prentice (2002) (conftype=loglog default option in SAS Proc LIFETEST) with back transformation to a CI on the untransformed scale. The estimate of the standard error will be computed using Greenwood’s formula.

DR will be displayed graphically and analyzed using Kaplan-Meier methodology. If the number of patients with uOR is small, the Kaplan-Meier method may not provide reliable estimates. In this case, only descriptive statistics or listings will be provided.

Frequency (number and percentage) of patients with each event type (PD or death) and censoring reasons will be presented by treatment arm. Reasons for censoring will be summarized according to the categories in Table 21 following the hierarchy shown.

**Table 21. DR Censoring Reasons and Hierarchy**

Hierarchy	Condition	Censoring Reason
1	No event and [withdrawal of consent date ≥ date of randomization OR End of study (EOS) = Patient refused further follow-up]	Withdrawal of consent
2	No event and lost to follow-up in any disposition page	Lost to follow-up
3	No event and [EOS present OR disposition page for any epoch after screening says patient will not continue into any subsequent phase of the study] and no adequate post-baseline assessment	No adequate post-baseline assessment
4	No event and none of the conditions in the prior hierarchy are met	Ongoing without an event

The DR time or censoring time and the reasons for censoring will also be presented in a patient listing.

#### 6.2.2.10. Time to response

Time to response (TTR) is defined, for patients with uOR, as the time from the date of randomization to the first documentation of objective response (uCR or uPR).

$$\text{TTR (in months)} = [\text{first date of uOR} - \text{date of randomization} + 1] / 30.4375$$

TTR will be summarized using simple descriptive statistics (mean, SD, median, min, max, Q1, Q3).

#### 6.2.3. PRO endpoints

The NCCN FHNSI-22 was developed using methods consistent with the Food and Drug Administration (FDA) PRO guidance (FDA, 2009) and surveyed input from patients with advanced cancers and physician experts (Cella D, et al., 2011). The FHNSI-22 questionnaire is specifically designed to be a stand-alone instrument to measure disease symptoms, treatment side effects and overall quality of life in patients with head and neck cancer.

Responses on the FHNSI-22 questionnaire are used to calculate a total score and scores for four subscales: TSE, DRS-P, DRS-E, and FWB. The questionnaire contains 22 items with 5-point Likert scales ranging from ‘not at all’ to ‘very much’. Higher scores mean better symptomatology, quality of life or functioning. The expected questionnaire completion time is about 5 minutes.

The EuroQol EQ-5D-5L is a patient-completed questionnaire designed to assess health status in terms of a single index value or utility score (Herdman M, et al., 2011). There are 2 components to the EuroQol EQ-5D-5L: a descriptive system in which individuals rate their level of problems (none, slight, moderate, severe, extreme/unable) in 5 areas (mobility, self-care, usual activities, pain/discomfort, and anxiety/depression) and a Visual Analogue Scale (VAS) in which patients rate their overall health status from 0 (worst imaginable) to 100 (best imaginable). Published weights are available that allow for the creation of a single summary score for the 5 Likert scale items. The expected questionnaire completion time is about 3 minutes or less.

All PRO summaries/analyses will be based on the FAS, with two analysis periods:

- Analysis including PRO data through EOT (including EOT)
- Additional analysis including all PRO data (including data collected after EOT)

#### **6.2.3.1. Instrument completion rate**

For each treatment arm and at each time point, the number and percentage of patients who complete the FHNSI-22 and EQ-5D-5L will be summarized, as will the reasons for non-completion of these measures.

#### **6.2.3.2. Descriptive summaries over time**

Only scheduled assessments will be included in the summaries that follow.

For each treatment arm and at each assessment time point, summary statistics of the FHNSI-22 total and subscale scores, the EQ-5D-5L, and VAS at each time point will be reported as described in Section 5.2.3.

For continuous endpoints (the total and subscale scores of the FHNSI-22, EQ-5D-5L, and VAS), change from baseline will be reported with N (number of non-missing values), mean, standard error, and 95% confidence intervals. Only patients with both a baseline score and a post-baseline score will be included in the summary of change from baseline scores.

Line charts depicting the means and mean changes of subscales together with standard error bars over time will be also provided.

#### **6.2.3.3. Time-to-event endpoints**

There are three separate time-to-event endpoints based on time to deterioration (TTD) of

- 1) HRQoL;
- 2) DRS-P;

3) 'swallowing'.

TTD is defined as the time from randomization to deterioration where deterioration is defined, respectively, as

- 1) a 3 point decrease on the FWB scale for health-related quality of life (HRQoL);
- 2) a 3 point decrease on the DRS-P for symptoms of disease;
- 3) a 1 point decrease, in two consecutive assessments, on the 'swallowing' item of the FHNSI-22.

The time to event for HRQoL and DRS-P will be calculated using the date of randomization and the date of the event, respectively. The time to event for "swallowing" will be calculated using the date of randomization and the date of the first of the two consecutive assessments used to identify the event. Note that a decline in FWB subscale of the FHNSI-22 represents a worsening in HRQoL. A decline in DRS-P score represents an increase in physical symptoms of disease. A decline in the 'swallowing' item score represents a decrease in the ability to swallow naturally and easily.

Patients who do not have a TTD event will be censored on the date when they last completed a PRO assessment.

TTD will be compared between treatment arms using a log-rank test stratified by randomization stratification factors. The treatment effect will be estimated using a Cox Proportional Hazard model stratified by the randomization strata to calculate the hazard ratio. Each stratum will define a separate baseline hazard function (using the 'STRATA' statement in SAS PROC PHREG), ie, for the i-th stratum the hazard function is expressed as:  $h(i;t) = h(i,0;t) \exp(x\beta)$ , where  $h(i,0;t)$  defines the baseline hazard function for the i-th stratum and  $x$  defines the treatment arm (0=Arm B, 1= Arm A) and  $\beta$  is the unknown regression parameter.

Ties will be handled by replacing the proportional hazards model by the discrete logistic model (Ties=Discrete option in SAS PROC PHREG).

Kaplan-Meier estimates (product-limit estimates) will be presented by treatment arm together with a summary of associated statistics including the median TTD time with 2-sided 95% CIs. In particular, the TTD rates at 12, 24, 36, 48, and 60 months will be estimated with corresponding 2-sided 95% CIs. The CIs for the median will be calculated according to Brookmeyer and Crowley (1982) and the CIs for the survival function estimates at the time points defined above will be derived using the log-log transformation according to Kalbfleisch and Prentice (2002) (conftype=loglog default option in SAS PROC LIFETEST) with back transformation to a CI on the untransformed scale. The estimate of the standard error will be computed using Greenwood's formula.

#### **6.2.3.4. Binary and categorical endpoint**

Responder is a patient with improvement in swallowing, defined as a 1 point increase on the 5-point Likert scale maintained for 2 consecutive assessments, in the single 'swallowing' item of the FHNSI-22, month 6 and 12 during the Maintenance Phase and also at EOT. In accordance with published recommendations (Osoba D, et al., 2005; Brundage M, et al.,

2007; Sloan JA, et al., 2007), proportions will be calculated including all patients with baseline questionnaires and counting those patients with missing questionnaires at a subsequent time point as not having improved.

Responder on the swallowing item of the FHNSI-22 will be compared between treatment arms using the Cochran-Mantel-Haenszel test stratified by randomization stratification factors. In this analysis, patients with missing questionnaires will be assigned as non-responder.

A sensitivity analysis will also be conducted. Patients whose post baseline questionnaires were missing because of disease progression or death will be considered as non-responder, with other patients whose post baseline questionnaires were missing being excluded from the analysis.

#### **6.2.3.5. Continuous endpoints**

Longitudinal random intercept random slope mixed-effect model will be carried out for the total and subscale scores of the FHNSI-22, EQ-5D-5L, and VAS using PROC MIXED. Outcomes are PRO post-baseline scores and the predictors are the corresponding baseline PRO score, treatment, randomization stratification factor, time (treated as a continuous variable), and treatment-by-time interaction. Intercept and time are considered as random effects particular to each patient. All available data for each patient should be used in the analyses. All parameter estimates should be obtained using restricted maximum likelihood. The unstructured covariance structure should be used to define covariance between random effects (using option “Type=UN” as a part of the RANDOM statement in PROC MIXED). For the degrees-of-freedom calculations the Kenward and Roger algorithm should be used (using option “ddfm = kr” as a part of the MODEL statement in PROC MIXED).

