### 3.8. Patient-Reported Outcomes

Patient-Reported Outcomes (PRO) will be assessed using the NCCN FHNSI-22 and the EQ-5D-5L. CCI [REDACTED] The maximum number of questions to be answered at any assessment is 30, so PRO collection is not expected to be burdensome to patients. The EQ-5D-5L will be administered to assess overall quality of life and to produce the utility values used for the economic model. The NCCN FHNSI-22 will be administered specifically to capture head and neck related (disease-related [DRS]) physical (DRS-P) and emotional symptoms (DRS-E), treatment side effects (TSE), and functional well-being (FWB), with a focus on the item “I can swallow naturally and easily.” CCI [REDACTED]

The EQ-5D-5L, FHNSI-22, CCI [REDACTED] will be administered on Day 1 of the Lead-in Phase (baseline); Days 1 and 29 of the CRT Phase; on Day 1 Cycle 1 and Day 1 Cycle 3 during the Maintenance Phase; then Q16W for 48 months, then Q24W until PD per modified RECIST v1.1. CCI [REDACTED]

CCI [REDACTED]

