### **5.5.2.4. Concurrent Radiation Therapy Adverse Events**

Grade 3 or 4 (CTCAE v4.03) therapy-induced mucositis and/or dysphagia, which are enhanced by cisplatin, are expected to develop in about two thirds of patients. Nutritional evaluation prior to the initiation of therapy for a prophylactic percutaneous endoscopic gastrostomy (PEG) tube placement is highly recommended. Placement of a feeding tube should be recorded, as should use of a feeding tube during and after treatment (eg, greater than or less than 50% of nutrition by tube). Other common radiation adverse events include: fatigue, weight loss, regional alopecia, xerostomia, hoarseness, transient ear discomfort, dysgeusia, and skin erythema and desquamation within the treatment fields.

Less common long-term treatment adverse events include: hypothyroidism, loss of hearing, chronic swallowing dysfunction requiring permanent feeding tube, and cervical fibrosis.

Much less common radiation adverse events include: mandibular osteoradionecrosis (<5% incidence), and cervical myelopathy (<1% with restriction of spinal cord dose to ≤45 Gy).

Treatment interruptions are allowed if there is symptomatic mucositis or skin reaction that, in the judgment of the clinician, warrants a break. For chemotherapy-attributable AEs requiring a break in treatment, IMRT may continue if clinically appropriate.

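### The linear treatment-by-time term in the PRO mixed model attenuates and misplaces an arm difference confined to one treatment phase, and no contrast is named

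*SAP*

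**What the plan says.** SAP 6.2.3.5 fits one mixed model to the FHNSI-22 total and subscale scores, the EQ-5D-5L and the VAS. On the outcome it states: "Outcomes are PRO post-baseline scores and the predictors are the corresponding baseline PRO score". The other predictors are treatment, the randomization stratification factor, and "time (treated as a continuous variable), and treatment-by-time interaction". On the random part: "Intercept and time are considered as random effects particular to each patient". No other form of time, no sensitivity model and no contrast or time point for the arm comparison is given.

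The assessments, after a baseline on Lead-in Day 1, are at "Days 1 and 29 of the CRT Phase; on Day 1 Cycle 1 and Day 1 Cycle 3 during the Maintenance Phase; then Q16W" (Protocol 3.8). That last interval holds until month 48, and assessments are less frequent from then on. SAP 6.2.3 asks for two analysis periods: through EOT, and all PRO data.

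Protocol 9.3.2.8 says only that arms are compared on mean scores from repeated-measures mixed models with baseline as covariate. It does not fix how time enters. SAP 6.2.3.2 plans by-arm summaries and changes from baseline at each time point, with confidence intervals and line charts, as description.

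**The concern.** With these terms, the arm difference that the model can express is a straight line in time: the treatment coefficient plus the interaction coefficient times t. The treatment coefficient alone is the difference extrapolated to time zero, before any post-baseline assessment.

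The design gives reason to doubt a straight line. Avelumab or placebo is given once in the Lead-in, three times during CRT, every 2 weeks for 12 months, and then not at all. An effect tied to CRT, or to being on avelumab, would be a pulse or a step. CRT is also when symptoms should be worst: Protocol 5.5.2.4 says that Grade 3 or 4 mucositis and/or dysphagia "are expected to develop in about two thirds of patients".

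At stake is a listed secondary objective, the effect of adding avelumab on symptoms and quality of life. Whether avelumab worsens symptoms during CRT is an obvious question for these data, and the Day 29 assessment is placed to answer it. It is also where this model can do worst.

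**Working it through.** The documents state no PRO mean, SD, target difference or power, so there is no figure of the plan's own to reproduce.

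**Inputs**
- Visit weeks from Lead-in Day 1, derived from the 7-day Lead-in, 63-day CRT Phase, 4-week cycles and 12-month Maintenance Phase: CRT Day 1 = 1; CRT Day 29 = 1 + 4 = 5; Maintenance C1 Day 1 = 1 + 9 = 10; C3 Day 1 = 10 + 8 = 18; then 34 and 50; EOT = 10 + 52 = 62. For all data the Q16W visits continue to 18 + 208 = 226. Assumed: visits on time, Q16W counted from C3 Day 1, later Q24W visits ignored.
- Size of 3 points: the deterioration threshold for FWB and DRS-P in SAP 6.2.3.3, used as a yardstick and not as a planned difference.

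**Formula.** The random effects have the same columns as the fixed time part (intercept and t). With the same complete visits in both arms, the expected estimate therefore equals the ordinary least-squares one, whatever the variances. For true differences d_j at visits t_j, the fitted difference at t is

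D(t) = Σ d_j × [1/n + (t − t̄)(t_j − t̄)/S], with S = Σ(t_j − t̄)².

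**Through EOT.** n = 7, t̄ = 180/7 = 25.71, S = 7950 − 180²/7 = 3321.4.
- True −3 at week 5 only: D(5) = −3 × [1/7 + (5 − 25.71)²/3321.4] = −3 × (0.1429 + 0.1292) = −0.82. About 73% is lost. Fitted values where the truth is zero: −0.89 (week 1), −0.72 (week 10), −0.57 (week 18), +0.25 (week 62).
- True +3 at weeks 18 to 62 only: D(62) = 3 × [4/7 + (62 − 25.71)(164 − 4 × 25.71)/3321.4] = 3 × (0.571 + 0.668) = 3.72, overstated. D(18) = 1.29, understated.

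**All data.** n = 17, t̄ = 1724/17 = 101.41, S = 266742 − 1724²/17 = 91908.
- True −3 at week 5 only: D(5) = −3 × (1/17 + 96.41²/91908) = −3 × (0.0588 + 0.1011) = −0.48. About 84% is lost.
- True +3 at weeks 18 to 66 only: 1.35 at week 18, 0.98 at week 66, and 1.48 at week 1 where the truth is zero.

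**Where the model is right.** A constant −3 is fitted as −3.00 at every visit, and a linearly changing difference is recovered exactly. A course shared by both arms subtracts out and gives 0.00 at every visit when dropout is equal. With an assumed 8-point dip and recovery, and dropout of 25% versus 5% per visit after week 10, it leaks about −0.01 at week 5 and −0.5 at week 62.

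**Incomplete data.** If patients leave the PRO schedule as the plan's PFS medians of 48.5 and 33 months imply, the Day 29 example gives about −0.85 (through EOT) and about −0.5 (all data). In one simulated data set with 10% dropout per visit, the linear model gave −1.04 at week 5 and a categorical-visit model −3.08.

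**Price of the alternative.** Assume between-patient SD 4, slope SD 0.03 per week, residual SD 4, 320 per arm, complete data and no baseline adjustment. The per-visit standard error is then about √[2 × (4² + 4²)/320] = 0.45, against about 0.36 at week 5 for the linear model.

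**The case against.** A growth-curve model is a standard choice, and the documents give no particular shape for the arm difference. Continuous time copes with CRT phases of varying length and with EOT assessments at patient-specific times; categorical visits need windows. The all-data schedule has 17 post-baseline visits to 48 months, so an unstructured covariance has 17 × 18/2 = 153 parameters under attrition. By-visit summaries (SAP 6.2.3.2) would show a separation at Day 29. The time-to-deterioration analyses and the swallowing responder analysis do not assume linear time. Formal error control covers only PFS and OS.

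Most of this stands and sets the priority. It does not remove the point. The by-visit summaries are unadjusted descriptions of each arm and not an arm contrast, and no other model compares the arms on continuous scores.

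A reader might also infer that a fall and recovery in both arms by itself distorts the comparison. The documents do not support that: a shared course cancels when follow-up is similar, and the fall and recovery is itself inferred from expected toxicity, not from any PRO data.

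**Conclusion.** The point holds in a limited form. The only model-based comparison of continuous PRO scores allows a straight-line arm difference and names no contrast. A difference confined to CRT Day 29 would be fitted at roughly a quarter of its size through EOT and a sixth with all data, with the rest assigned to other visits. The same truth also gives different answers in the two required analysis periods.

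With complete visits these fractions depend only on the visit grid and the shape of the true difference. That shape is an assumption, and the standard errors rest on assumed SDs.

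Two wider readings do not hold. The model does not shrink differences in general: constant and linear ones are recovered and some late ones are overstated. Nor is it uninformative at every time. No alpha is attached to this secondary analysis and PFS and OS are untouched, so the change is worth making at modest priority.

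**What to change.** Change SAP 6.2.3.5 so that the main model has:
- time as categorical visit (or as treatment phase), with treatment interaction, baseline score and stratification factors;
- Kenward-Roger degrees of freedom, as already planned, and an unstructured within-patient covariance with a stated fallback if it does not converge;
- named contrasts: the arm difference at CRT Day 29 and the arm difference averaged over Maintenance;
- windows that assign each assessment, including EOT and unscheduled ones, to a visit, and a rule to pool or truncate sparse late visits.

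Keep the linear random-slope model as supportive.

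The cost is SAP text and programming within the same SAS procedure, the window definitions, and somewhat less precision per visit (about 0.45 against 0.36 under the assumed SDs). No new data are needed.

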#### **6.2.4. Pharmacokinetic endpoints**

The following pharmacokinetic analyses will be based on the PK analyses set by treatment arm.

##### **6.2.4.1. Avelumab**

$C_{\text{trough}}$  and  $C_{\text{max}}$  for avelumab will be summarized descriptively (n, mean, SD, CV, median, minimum, maximum, geometric mean, its associated CV, and 95% CI) by treatment phase, cycle (if applicable), and day in Arm A. Other standard parameters will be calculated, including but not limited to single and multiple dose  $T_{\text{max}}$ ,  $T_{\text{ss,max}}$ , as data permit.

$C_{\text{trough}}$  and  $C_{\text{max}}$  for avelumab will be plotted for each dose using a box whisker plot by treatment phase, cycle (if applicable), and day within in order to assess the attainment of steady state in Arm A.

Additionally, avelumab PK will be evaluated following cisplatin dosing by comparing the overall geometric mean ratios of  $C_{\text{max}}$  and  $C_{\text{trough}}$  in only Arm A on Day 8 of the CRT Phase to Day 1 of the Lead-in Phase.

Pharmacokinetic parameters for avelumab will be taken from observed values or derived from plasma concentration-time data as described in Section 3.2.4.

